6.2.2. Analysis Methods for Secondary Efficacy Endpoints

The analyses for the secondary efficacy endpoints will be conducted using the FAS, unless otherwise specified. Specifically, for endpoints including ALT normalization, the subset of subjects in the FAS with baseline abnormal ALT will be used, for HBeAg loss and HBeAg seroconversion, the Serologically Evaluable FAS for HBeAg Loss/Seroconversion will be used, and for HBsAg loss and HBsAg seroconversion, the Serologically Evaluable FAS for HBsAg Loss/Seroconversion will be used.

Normal ALT and normalization of ALT analyses will each be repeated twice, once using the central laboratory ULN and once using the AASLD ULN.

Categorical secondary efficacy endpoints will be summarized by number and percentage of subjects that meet the endpoint, and a two-sided CMH test stratified by age at baseline (< 6 vs. ≥6 years) and region (North America/Europe vs Asia) will be performed. Analyses will also be repeated using the M = F and the M = E approach.

Incidence of drug resistant mutations will be reported in a separate virology report. The virology team may be unblinded in advance to identify which samples are required for analysis.

In addition, log₁₀ HBV DNA (IU/mL), ALT (U/L) and log₁₀ HBsAg (IU/mL), and corresponding change from baseline values, will be summarized by visit using observed data. P-values will be calculated using the two-sided Wilcoxon rank-sum test.

The proportion of subjects with HBV DNA < 69 IU/mL [400 copies/mL] using both the M = F and M = E approach, proportion of subjects with HBeAg seroconversion using the M=F approach only, proportion of subjects with normalized ALT by central lab and AASLD normal ranges, mean log₁₀ HBV DNA (IU/mL), mean log₁₀ HBsAg (IU/mL), and mean ALT (U/L) will be plotted with 95% CIs over time. Supportive listings for the analyses of the secondary endpoints will also be generated.

6.3. Sensitivity Analysis of Secondary Efficacy Endpoints

For the following non-composite secondary efficacy endpoints, additional sensitivity analyses will be performed using only the subset of subjects who completed the Week 48 assessment or prematurely discontinued from blinded study drug prior to Protocol Amendment 3 (same as Group1 defined in Section 6.1.5):

- proportion of subjects with HBeAg seroconversion in the Serologically Evaluable FAS for HBeAg Loss/Seroconversion.
- proportion of subjects with HBeAg loss in the Serologically Evaluable FAS for HBeAg Loss/Seroconversion.
- proportion of subjects with normal ALT and normalization of ALT

- proportion of subjects with HBV DNA < 29 IU/mL [169 copies/mL]
- proportions of subjects with HBsAg loss and seroconversion in the Serologically Evaluable FAS for HBsAg Loss/Seroconversion

Both a $M = F$ and $M = E$ approach will be used, and p-values will be reported up to Week 72.

6.4. Changes From Protocol-Specified Efficacy Analyses

The protocol specifies that the analysis of the primary efficacy endpoint will evaluate the difference between the TDF and placebo treatment groups using a two-sided Fisher's exact test. This has been modified to a CMH test, controlling for the age group at baseline and region, in order to account for the stratified randomization used in the study. The age group at baseline was specified as <6 vs. ≥6 years, compared to the randomization strata age group of 2 to <6 and 6 to <12 years, as some subjects were age 12 by baseline. This change was also made for the analyses of the secondary endpoints. The two-sided Fisher's exact test will still be performed as a secondary analysis of the primary endpoint.

The PP Analysis Set, Serologically Evaluable FAS for HBeAg Loss/Seroconversion, and Serologically Evaluable FAS for HBsAg Loss/Seroconversion, was not defined in the protocol, but was added in the SAP.

For HBV DNA analyses, the default will be to report measurements in IU/mL, which is the current clinically accepted way to describe this parameter, instead of copies/mL.

For ALT normalized and normal analyses, both the AASLD and central lab normal ranges will be used.

7. SAFETY ANALYSES

For the Week 48 analysis, unless otherwise specified, safety data will be summarized for the double-blind phase only and p-values will be calculated up to Week 48 for by-visit summaries. All safety data up to the Week 48 data cut, including data collected during open-label phase and TFFU phase will be included in data listings.

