8.9. Safety Analysis

All safety data collected on or after the date that study drug was first dispensed will be summarized by randomized treatment group. Data for the pretreatment and treatment-free follow-up periods will be included in listings.

The proportion of subjects in each treatment group with an AE leading to permanent discontinuation of study drug through Week 48 (also at Weeks 144 and 192) will be summarized.

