1.1. Study Objectives

The primary objective of this study is:

- To evaluate the antiviral efficacy at Week 48 of tenofovir disoproxil fumarate (TDF; Viread®) versus placebo in pediatric subjects (aged 2 to < 12 years) with chronic hepatitis B infection

The key secondary objective is:

- To evaluate the proportion of subjects with hepatitis B e antigen (HBeAg) seroconversion at Week 48 (in subjects with baseline HBeAg sero-positivity)

Other secondary objectives are:

- To characterize the safety and tolerability profile of TDF at Week 48 in pediatric subjects (aged 2 to < 12 years) with chronic hepatitis B infection
- To evaluate the biochemical and serological responses at Week 48 to TDF versus placebo
- To evaluate the incidence of potential resistance mutations to TDF at Week 48 in the hepatitis B virus (HBV) polymerase/reverse transcriptase (pol/RT)
- To assess the pharmacokinetics (PK) of tenofovir in subjects receiving the tablet formulation and those receiving the oral powder formulation

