At screening, pediatric subjects (2 to < 12 years of age) with chronic HBeAg-positive or HBeAg-negative HBV infection (hepatitis B surface antigen [HBsAg]-positive for at least 6 months; with HBV DNA $\geq 10^5$ copies/mL, ALT $\geq 1.5 \times$ ULN and creatinine clearance ≥ 80 mL/min/1.73 m² at screening by the Schwartz formula) will be eligible for the study. Subjects must be naive to TDF, but could have received interferon-alfa and/or other oral anti-HBV nucleoside/nucleotide therapies. Subjects experienced on oral anti-HBV nucleoside/nucleotide therapy must have discontinued therapy ≥ 16 weeks prior to screening (in order to avoid on-treatment ALT flare if randomized to receive placebo treatment). Subjects must have discontinued interferon-alfa ≥ 6 months prior to screening. Subjects must be without evidence of co-infection with human immunodeficiency virus (HIV), hepatitis C virus (HCV), hepatitis D virus (HDV) or acute hepatitis A virus (HAV). Subjects with a history of significant renal disease, bone disease, decompensated liver disease, evidence of hepatocellular carcinoma (ie, α fetoprotein > 50 ng/mL), or any chronic liver disease not related to HBV infection will not be eligible for the study.

Study Periods/Phases

The duration of randomized, double-blind treatment is 48 weeks.

As per Protocol Amendment 4, after 48 weeks of blinded randomized treatment, each subject will switch to open-label TDF treatment for an additional 144 weeks (ie through Week 192). Subjects under Protocol Amendment 3, wherein the primary analysis was planned for Week 72, who were treated beyond Week 48 of blinded randomized treatment, were to switch to open-label TDF at the Week 72 visit and then continue on open-label treatment until Week 192. Total study drug treatment period is 192 weeks for all enrolled subjects.

After the completion of the Week 192 visit, all subjects who have completed the study will be offered open-label TDF under the Extension Phase of the protocol. Subjects who permanently discontinue study drug or complete the study at Week 192 and do not enter the Extension Phase will be followed for 24 weeks off treatment or up to initiation of active treatment, whichever occurs first. Subjects who enter the Extension Phase after completion of the study at Week 192 will be offered open label TDF and followed every 12 weeks until TDF is commercially available in that country for treatment of chronic HBV in subjects of their age and weight.

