4.3.1. Duration of Exposure to Blinded Study Drug

Duration of exposure to blinded study drug will be defined as (last dose date of blinded study drug – first dose date of blinded study drug + 1 day), regardless of temporary interruptions in study drug administration, and will be expressed in weeks (recorded to 1 decimal place, eg, 4.5 weeks). Please refer to Section 3.8.1 for details on the definition of the last dose date of blinded study drug.

Duration of exposure to blinded study drug will be summarized using descriptive statistics (sample size, mean, SD, median, Q1, Q3, minimum, and maximum) and as the number and percentage of subjects exposed for specified periods, eg, ≥ 4 weeks (28 days), ≥ 8 weeks (56 days), ≥ 16 weeks, ≥ 24 weeks, ≥ 32 weeks, ≥ 40 weeks, ≥ 48 weeks, ≥ 56 weeks, ≥ 64 weeks, and up to ≥ 72 weeks.

Summaries will be provided by treatment group for subjects in the Safety Analysis Set. No inferential statistics will be provided.

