4.3.2. Adherence with Blinded Study Drug Regimen

The amount of blinded study drug dispensed and returned was captured on the Study Drug Accountability form. Adherence will be summarized for blinded study drug during both the double-blind phase (eg. some subjects took blinded study drug up to Week 72, while some subjects only took blinded study drug up to Week 48) and up to Week 48 only. To determine adherence up to Week 48, only records in the Study Drug Administration eCRF prior to the Week 48 Protocol Visit will be used.

Adherence (%) with blinded study drug will be calculated as follows:

$$\text{Adherence (\%)} = 100 \times \frac{\text{Amount of Blinded Study Drug Taken [1]}}{\text{Amount of Blinded Study Drug Expected To Be Prescribed [2]}}$$

If calculated adherence is greater than 100%, then adherence will be set to 100%.

A dispensation period will be defined as a single entry into the Study Drug Administration eCRF. If any blinded study drug bottle is not returned or unknown (missing return date or ongoing) or the amount of blinded study drug dispensed is missing, then all of the records for the corresponding dispensation period will be excluded from both denominator and numerator in the calculation. For a dispensation period where the amount of blinded study drug returned is missing (but a date of return is available), it is assumed the amount of blinded study drug returned is zero.

[1] Amount of blinded study drug taken is determined by first converting the amount of blinded study drug from the powder or tablet formulation into mg of TDF or matching placebo, then subtracting the total amount of blinded study drug returned from the total amount of blinded study drug dispensed.

Specifically, if blinded study drug is administered as the powder formulation, then the amount of blinded study drug is multiplied by 40 (ie, 40 mg of blinded study drug per 1 gram of powder). If blinded study drug was administered as the tablet formulation, then the amount of blinded study drug is multiplied by 150 mg, 200 mg, 250 mg or 300 mg as indicated by the dose unit of blinded study drug dispensed. After conversion, the total amount of blinded study drug taken is calculated as the total amount of blinded study drug dispensed (mg) across all dispensation periods minus the total amount of blinded study drug returned (mg) across all dispensation periods.

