7.1.5. Treatment-Emergent AEs

7.1.5.1. Definition of Treatment Emergent

Treatment-emergent AEs will be defined for the double-blind phase and the open-label phases separately.

Treatment-emergent AEs occurring during the double-blind phase are defined as:

- Any AE with onset date on or after the blinded study drug start date and no later than the minimum of the blinded study drug stop date + 3 days and the first dose date of open-label study drug, if applicable, for those who discontinued blinded study drug permanently, or
- Any AE with onset date on or after the blinded study drug start date for those who are still on the blinded study drug, or
- Any AE leading to blinded study drug discontinuation.

Treatment-emergent AEs occurring during the open-label phase are defined as:

- Any AE with onset date on or after the open-label study drug start date and no later than the open-label study drug stop date + 3 days for those who discontinued open-label TDF permanently, or
- Any AE with onset date on or after the open-label study drug start date for those who are still on open-label study drug, or
- Any AE leading to open-label study drug discontinuation.

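### In the Week 48 analysis, the safety tables that count events at any time mix 48-week and 72-week blinded follow-up, with no Week 48 cut and no exposure-adjusted rate

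*SAP*

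**What the plan says.** SAP section 7 sets the reporting period for the Week 48 analysis: "safety data will be summarized for the double-blind phase only". The same sentence applies a Week 48 limit only to the p-values of by-visit summaries, not to the counting of events.

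The event definitions follow the same pattern. A treatment-emergent AE in the double-blind phase (SAP 7.1.5.1) has its onset on or after the first blinded dose and, for those who have stopped blinded drug, "no later than the minimum of the blinded study drug stop date + 3 days and the first dose date of open-label study drug". Graded and marked laboratory abnormalities (SAP 7.2.2.1 and 7.2.2.2) use the same end point. ALT flare (SAP 7.2.3) and confirmed renal abnormalities (SAP 7.4.2) are also summarised over the double-blind phase.

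The length of that phase differs between children. Those under Amendment 3 "who were treated beyond Week 48 of blinded randomized treatment, were to switch to open-label TDF at the Week 72 visit" (SAP 1.2). SAP 4.3.2 says that "some subjects took blinded study drug up to Week 72, while some subjects only took blinded study drug up to Week 48", and the exposure table in SAP 4.3.1 runs to "≥ 48 weeks, ≥ 56 weeks, ≥ 64 weeks, and up to ≥ 72 weeks".

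Three statements tie safety to Week 48:
- Protocol 8.9 asks for the proportion of subjects "with an AE leading to permanent discontinuation of study drug through Week 48".
- The Statistical Methods part of the protocol synopsis has the proportions with an AE or an abnormal laboratory test summarised at Weeks 48, 144 and 192.
- SAP 1.1 gives as an objective "To characterize the safety and tolerability profile of TDF at Week 48 in pediatric subjects".

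SAP 7.11 lists changes from the protocol's safety analyses. It covers the 3-day extension of the treatment-emergent window but not the counting period.

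**The concern.** The percentage of children with at least one event depends on how long they are watched. When some are watched for 48 weeks and others for up to 72, the table estimates neither a 48-week nor a 72-week risk. Its value depends on how many children had passed Week 48 when the amendment took effect, which is a fact about enrolment timing and not about the drug.

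A reader of a Week 48 report is likely to take the AE and laboratory percentages, and the risk differences built from them, as roughly one-year figures. One figure that the protocol asks for by name, AE discontinuations through Week 48, would not be available at all. The SAP recognises the problem elsewhere: adherence is given both for the whole phase and up to Week 48 (4.3.2), missing-equals-failure efficacy summaries stop at Week 48 (6), and Tanner staging is handled by amendment group (7.5). The event tables have no such split, and neither document plans an exposure-adjusted rate or a time-to-event summary for AEs.

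**Working it through.** **Which tables are affected.** SAP section 7 separates into two kinds of summary.

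| Kind of summary | SAP sections | Is a Week 48 figure available? |
|---|---|---|
| Any event in the phase: AEs, SAEs, AE discontinuations, graded and marked laboratory abnormalities, ALT flare, confirmed renal abnormalities | 7.1.6, 7.2.2, 7.2.3, 7.4.2 | No, counted to the end of blinded drug |
| By visit: numeric laboratory values, BMD change and decreases of at least 4%, bone markers, eGFR | 7.2.1, 7.3.1, 7.3.2, 7.4.1 | Yes, as the Week 48 row |

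The concern reaches only the first row.

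**Inputs.** The documents give the two blinded durations, 48 and 72 weeks, a ratio of 72/48 = 1.5. They state no safety event rate and no share of children treated blinded to Week 72, so there is no figure of the plan's own to reproduce. Both are assumed below.

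**Formulae.** Let r48 be the 48-week risk and s the share of children with 72 blinded weeks. With a constant hazard (assumed):

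- r72 = 1 − (1 − r48)^1.5
- reported percentage = (1 − s) × r48 + s × r72

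For r48 = 10%: r72 = 1 − 0.9^1.5 = 0.1462. With s = 25%, the table shows 0.75 × 0.10 + 0.25 × 0.1462 = 11.2%.

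| True r48 | r72 | s = 25% | s = 50% | s = 75% |
|---|---|---|---|---|
| 10% | 0.1462 | 11.2% | 12.3% | 13.5% |
| 20% | 0.2845 | 22.1% | 24.2% | 26.3% |
| 40% | 0.5352 | 43.4% | 46.8% | 50.1% |

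The r72 column is the ceiling, reached if every child had 72 weeks.

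**Risk difference.** If the true 48-week risks were 20% and 10%, a difference of 10 points, equal shares of 50% in both arms would give 24.2 − 12.3 = 11.9 points. The difference is rescaled by the longer follow-up; it is not created by it.

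**Effect of chance imbalance.** With equal hazards in both arms and shares of 60% and 40% (assumed), the spurious difference is 0.2 × (r72 − r48): 0.2 × 4.6 = 0.9 points at a 10% risk, 0.2 × 8.45 = 1.7 at 20%, and 0.2 × 13.5 = 2.7 at 40%. Randomisation makes no such imbalance expected.

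**Clue to the share.** SAP 6.1.5 withholds p-values for Group 2 (reached Week 48 or stopped after Amendment 3) and Group 3 because they are small. If Group 2 is small among the 89 treated children, most belong to the 72-week schedule. Group 3, also called small, includes the Group 1 children who stopped early, so those are few. This points to the upper part of the range, but no count is given.

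**The case against.** The strongest reply is that the protocol contains no general Week 48 cut. Protocol 8.9.2 defines treatment-emergent AEs from drug start to drug stop, 8.9.3 counts laboratory abnormalities at any time after baseline, and 8.6.1.2 brings all collected data into the safety summaries. The synopsis wording names Weeks 48, 144 and 192, which are also the analysis times, so it may name the analysis and not an event window. The protocol's statistical section specifies no ALT flare or confirmed renal abnormality table. A reader might infer that the protocol asks for all of these proportions through Week 48; the documents do not support that. Only the request for AE discontinuations in 8.9 is explicit. This part of the reply stands.

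It also stands that the safety endpoints the protocol names for Week 48, both on lumbar spine BMD, are tabulated by visit. The SAP states the double-blind period openly, and it reports completion at Week 48 and at Week 72 (4.2) and exposure duration by arm (4.3.1). But an exposure table cannot show which events began after Week 48.

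Finally, whole-phase counting uses all the placebo-controlled data from 89 treated children, which matters for rare renal and hepatic events. That is a good reason to keep those tables. It is not a reason to leave out the Week 48 figures.

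**Conclusion.** The concern holds within limits. The any-event safety tables in the Week 48 analysis mix 48- and 72-week risks, and no exposure-adjusted rate is planned that would make them interpretable. The SAP does not deliver the AE discontinuation proportion through Week 48 that protocol 8.9 requests. It also may not deliver the Week 48 AE and laboratory proportions in the synopsis, depending on how that sentence is read. SAP 7.11 is silent on the difference.

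A reader might infer that the comparison between arms is biased. The documents do not support this: both arms are counted over the same phase, and randomisation should balance the exposure mix. What is affected is the meaning of the absolute percentages and of the risk differences.

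The size cannot be fixed from the documents. With a constant hazard and 25% to 75% of children at 72 weeks, both assumed, a 10% risk at 48 weeks would read as 11.2% to 13.5% and a 20% risk as 22.1% to 26.3%. If the 72-week share is very high, the tables come close to a single 72-week risk, and labelling becomes the main issue.

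**What to change.** 1. Keep the whole double-blind tables. Label them as covering up to 72 weeks of blinded treatment, and add subject-years and events per subject-year by arm.
2. Add AE, AE-discontinuation and graded laboratory tables that count events up to the Week 48 visit, or up to last blinded dose + 3 days or first open-label dose if either is earlier.
3. Record the counting period in SAP 7.11, so that the relation to protocol 8.9 and the synopsis is explicit.

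This needs a date filter on data already held and one repeated set of tables; no new data are collected. Replacing the whole-phase tables as the main display is not necessary and would move some placebo-controlled events out of view.

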7.1. Adverse Events

7.1.1. Adverse Event Dictionary

Clinical and laboratory adverse events (AEs) will be coded using the current version of MedDRA. System organ class (SOC), high-level group term (HLGT), high-level term (HLT), preferred term (PT), and lower-level term (LLT) will be provided in the AE dataset.

7.1.2. Adverse Event Severity

Adverse events are graded by the investigator as Grade 1 (mild), Grade 2 (moderate), Grade 3 (severe) or Grade 4 (life threatening) according to toxicity criteria specified in the protocol. The severity grade of events for which the investigator did not record severity will be categorized as “missing” for tabular summaries and data listings. The missing category will be listed last in summary presentation.

7.1.3. Relationship of Adverse Events to Study Drug

Related AEs are those for which the investigator selected “Related” on the AE eCRF to the question of “Related to Study Treatment.” Relatedness will always default to the investigator’s choice, not that of the medical monitor. Events for which the investigator did not record relationship to study drug will be considered related to study drug for summary purposes. However, by-subject data listings will show the relationship as missing.

7.1.4. Serious Adverse Events

Serious adverse events (SAEs) will be identified and captured as SAEs if the AEs met the definitions of SAEs that were specified in the study protocol. SAEs captured and stored in the clinical database will be reconciled with the SAE database from the Gilead Drug Safety and Public Health Department before data finalization.

7.1.5. Treatment-Emergent AEs

7.1.5.1. Definition of Treatment Emergent

Treatment-emergent AEs will be defined for the double-blind phase and the open-label phases separately.

Treatment-emergent AEs occurring during the double-blind phase are defined as:

- Any AE with onset date on or after the blinded study drug start date and no later than the minimum of the blinded study drug stop date + 3 days and the first dose date of open-label study drug, if applicable, for those who discontinued blinded study drug permanently, or
- Any AE with onset date on or after the blinded study drug start date for those who are still on the blinded study drug, or
- Any AE leading to blinded study drug discontinuation.

Treatment-emergent AEs occurring during the open-label phase are defined as:

- Any AE with onset date on or after the open-label study drug start date and no later than the open-label study drug stop date + 3 days for those who discontinued open-label TDF permanently, or
- Any AE with onset date on or after the open-label study drug start date for those who are still on open-label study drug, or
- Any AE leading to open-label study drug discontinuation.

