Study GS-US-104-0321 enrolled antiretroviral treatment-experienced HIV-1 infected adolescents that were treated with tenofovir DF or placebo in addition to a reconfigured and optimized background regimen (OBR) for 48 weeks. The Week 48 results of this study showed that adolescents in both treatment groups demonstrated a virologic response to treatment. There were no statistically significant differences between tenofovir DF and placebo groups for any of the efficacy endpoints for the ITT analysis set. Treatment response was demonstrated by reductions in viral load and increases in CD4 cell count in both treatment groups. Analyses of the primary efficacy endpoint using the subgroup of subjects with a maximum of 1 active drug in their OBR (ANRS scoring system) and confirmation using post hoc analyses (Stanford database scoring system; 3- and 5-point scales) provide evidence for the antiretroviral activity of tenofovir DF in HIV-1 infected adolescents.

The development of virological resistance in these antiretroviral-experienced adolescents with extensive resistance in their HIV at screening was comparable to that observed in heavily treatment-experienced adults. Mutation K65R developed in one subject in the tenofovir DF group.

Tenofovir DF was generally safe and well tolerated when given in combination with an OBR in this study. The safety profile in adolescent subjects with HIV-1 infection was consistent with the known safety profile in adults; the most marked differences between tenofovir DF and placebo groups in reported AEs were for mild to moderate gastrointestinal disorders (vomiting, nausea, and diarrhea). No deaths or SAEs considered related to study drug were reported, and only 1 subject discontinued due to an AE (vomiting). There was no evidence of compromised renal function due to tenofovir DF.

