3.1.2. Safety Analysis Set

The Safety Analysis Set will include all randomized subjects who have received at least 1 dose of study drug. Subjects will be analyzed according to the treatment they actually received during the double-blind phase. The actual treatment received will differ from the randomized treatment only when their actual treatment differs from randomized treatment for the entire double-blind treatment duration. This is the primary analysis set for safety analyses.

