7.1.6. Summaries of AEs and Deaths

For the Week 48 analysis, the treatment-emergent AEs occurring during the double-blind phase will be summarized based on the Safety Analysis Set.

A brief summary of AEs (ie, the number and percentage of subjects) will be presented by treatment group for the double-blind phase for the following: (1) any treatment-emergent AE, (2) any Grade 3 or 4 treatment-emergent AE, (3) any Grade 2, 3, or 4 treatment-emergent AE, (4) any treatment-emergent AE related to study drug, (5) any Grade 3 or 4 treatment-emergent AE related to study drug, (6) any Grade 2, 3, or 4 treatment-emergent AE related to study drug, (7) any treatment-emergent SAE, (8) any treatment-emergent SAE related to study drug, (9) any treatment-emergent AE leading to premature discontinuation of study drug, (10) any treatment-emergent AE leading to temporary study drug interruption, and (11) any death.

Treatment-emergent death occurring during the double-blind phase refers to death that occurs between the first dose date of blinded study drug to the minimum of the last dose date of blinded study drug + 3 days and the first dose date of open-label study drug, if applicable, for those who discontinued blinded study drug permanently. Treatment-emergent death occurring during the open-label phase refers to death that occurs between the first dose date of open-label study drug to the last dose date of open-label study drug + 3 days.

Summaries (number and percentage of subjects) of AEs (by SOC, HLT [if specified below], and PT) will be provided by treatment group and overall using the Safety Analysis Set for the double-blind phase as follows:

- All treatment-emergent AEs summarized by SOC, HLT, and PT
- Any Grade 3 or 4 treatment-emergent AEs
- Any Grade 2, 3, or 4 treatment-emergent AEs
- All treatment-emergent nonserious AEs occurring in at least 5% of subjects in any treatment group (this summary is generated per requirement for reporting in ClinicalTrials.gov)
- All treatment-emergent treatment-related AE summarized by SOC, HLT, and PT
- Any Grade 3 or 4 treatment-emergent treatment-related AEs
- Any Grade 2, 3, or 4 treatment-emergent treatment-related AEs
- All treatment-emergent SAEs
- All treatment-emergent treatment-related SAEs
- All treatment-emergent AEs leading to premature discontinuation from study drug
- All treatment-emergent AEs leading to temporary interruption of study drug

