7.11. Changes From Protocol-Specified Safety Analyses

Baseline for BMD assessments for spine and whole body (via DXA scan) and serum bone biochemical markers will be calculated only using the Baseline Visit value, instead of taking the mean of the Screening and Baseline Visit values.

Treatment-emergent AEs and lab abnormalities were defined as any AE or lab abnormality that began on or after the study drug start date and no later than the study drug stop date in the protocol for those who discontinued study drug. This has been updated in this SAP to any AE with onset date on or after the blinded study drug start date and no later than the minimum of the blinded study drug stop date + 3 days and the first dose date of open-label study drug, if applicable for the double-blind phase, and to any AE with onset date on or after the open-label study drug start date and no later than the minimum of the open-label study drug stop date + 3 days for the open-label phase. This change was made as labs performed 1-2 days after study drug stopped were being excluded causing the measurement for the timepoint to be missed, even though protocol specified visit windows allowed for labs to be performed in a short period after the study drug was stopped.

Percent change from baseline in bone mineral density of lumbar spine was compared between treatment groups using ANOVA with treatment as a fixed effect, instead of the Wilcoxon rank sum test, to be consistent with other studies.

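### The double-blind adverse event window includes the first open-label dose date, so a placebo child's first-day TDF event can be tabulated under placebo

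*SAP*

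**What the plan says.** For subjects who have stopped blinded drug, SAP 7.1.5.1 accepts an AE as double-blind treatment-emergent if its onset is "no later than the minimum of the blinded study drug stop date + 3 days and the first dose date of open-label study drug". The open-label definition in the same section begins with "Any AE with onset date on or after the open-label study drug start date". Neither definition says which phase takes an event that meets both.

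SAP 1.2 states that after blinded treatment "each subject will switch to open-label TDF treatment for an additional 144 weeks", so placebo children receive their first TDF dose at this point.

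Three further rules decide where such an event is reported at Week 48:

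- SAP 7.1.6: "the treatment-emergent AEs occurring during the double-blind phase will be summarized based on the Safety Analysis Set".
- SAP 3.1.2: "Subjects will be analyzed according to the treatment they actually received during the double-blind phase".
- SAP 7: "All safety data up to the Week 48 data cut, including data collected during open-label phase and TFFU phase will be included in data listings".

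SAP 7.11 explains why the protocol's window, which ended at the study drug stop date, was extended: "This change was made as labs performed 1-2 days after study drug stopped were being excluded".

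**The concern.** An AE that starts on the day of the first open-label dose may follow that dose. In a placebo child it would then be an event on TDF. The rule still puts it in the double-blind tables, in the placebo column, and the Week 48 report has no open-label table to balance it.

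The two arms are not affected alike. A TDF-arm child's event on that day is attributed to TDF, which is the drug the child has been taking throughout. Only the placebo column can receive events caused by the other treatment. What is at stake is the controlled AE comparison in children aged 2 to under 12, where a true TDF excess could look smaller than it is.

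The stated reason for extending the window concerns laboratory samples lost after drug was stopped. That supports the 3 extra days. It does not explain why the first TDF day should count as blinded time for AEs.

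**Working it through.** The documents give no figure for this, so there is none to reproduce. The check has three parts.

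**1. The date rule.** Set the blinded stop date to day 0 and let the first open-label dose fall on day g. The current upper bound for a double-blind AE is min(3, g). With the window closed the day before the first open-label dose, it is min(3, g − 1). An AE with onset on day g falls as follows:

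| g (days) | Current bound | Double-blind now? | Open-label now? | Changed bound | Double-blind after change? |
|---|---|---|---|---|---|
| 0 | 0 | yes | yes | −1 | no |
| 1 | 1 | yes | yes | 0 | no |
| 2 | 2 | yes | yes | 1 | no |
| 3 | 3 | yes | yes | 2 | no |
| 4 | 3 | no | yes | 3 | no |
| 5 | 3 | no | yes | 3 | no |

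The overlap exists when open-label dosing starts 0 to 3 days after the blinded stop, which is the expected case for a direct switch. With a gap of 4 days or more, the 3-day limit already excludes the event.

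**2. The weight of one child.** SAP 1.3 gives 89 treated subjects and 2:1 allocation but no arm counts. 89/3 = 29.7, so about 30 placebo children are assumed. The range shown runs from 29 to the originally planned 33.

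- One affected child: 1/33 = 3.0, 1/30 = 3.3, 1/29 = 3.4 percentage points.
- Two affected children: 2/33 = 6.1, 2/30 = 6.7, 2/29 = 6.9 percentage points.

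These are maxima. SAP 7.1.6 counts a subject once per summary, so a child who already had that term during blinded treatment adds nothing. Two children with no earlier event of a nonserious term would by themselves bring it above the 5% threshold that SAP 7.1.6 sets for the registry table.

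**3. How the SAP treats the same day elsewhere.**

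- Adherence (SAP 4.3.2): each blinded dispensing period ends on the day before a minimum that includes the first open-label dose date. The switch day is therefore not blinded exposure.
- Open-label baseline (SAP 3.8.1): values up to and including Open-Label Study Day 1 qualify as baseline. Laboratory values from that day are in effect treated as preceding TDF.
- AEs (SAP 7.1.5.1): the switch day is inside the blinded window.

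The AE rule thus conflicts with the SAP's own exposure convention. The inclusive bound fits the handling of laboratory values, but that logic does not carry over to an AE onset date.

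**The case against.** Only one calendar day is affected, out of at least 336. The minimum in SAP 7.1.5.1 already removes the larger problem by cutting the 3-day tail at the switch. The event also remains an open-label event, and all AEs are listed, so switch-day onsets can be traced. SAP 7.1.6 plans counts and percentages with no between-arm AE test, and no efficacy endpoint or decision rule is touched. Protocol 7.2 lists a start date for each AE but no onset time, so any date rule will misplace some events. All of this stands, and it limits the importance of the point. It does not justify the rule that assigns the ambiguous events to placebo.

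A reader might infer three stronger things that the documents do not support.

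- **A sizeable shift in gastrointestinal rates.** Protocol 1.2.3.1.9 reports that "the most marked differences between tenofovir DF and placebo groups in reported AEs were for mild to moderate gastrointestinal disorders". That was a 48-week study in treatment-experienced HIV-1-infected adolescents on an optimized background regimen. The text gives no rates and no first-day onsets, so no first-day rate for this trial can be drawn from it.
- **That every switching placebo child is exposed to the rule.** It applies only when the gap is 3 days or less.
- **That Week 48 samples are known to be drawn before the first open-label dose.** Protocol 6.2.2 lists sampling and dispensing but does not say when that dose is taken. The order is a reasonable inference and no more.

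**Conclusion.** The point holds as a small, one-directional flaw in the AE phase definition. When open-label TDF starts within 3 days of the blinded stop date, an AE with onset on the first open-label day is counted in both phases, and the Week 48 tables show it only under the blinded-phase treatment. For a placebo child this can only raise the placebo rate and narrow a TDF excess.

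The size cannot be determined from the documents and may be zero. The upper limit is about 3.3 percentage points per affected child and term. That figure rests on about 30 treated placebo children and on the child having had no earlier event of that term. The correction is worth making because it is cheap and the direction of error is known, not because a large distortion has been shown.

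**What to change.** - **SAP 7.1.5.1:** for AEs, close the double-blind window at the earlier of blinded stop date + 3 days and the day before the first open-label dose date. Assign switch-day onsets to the open-label phase and flag them in the AE listing. The separate criterion for AEs leading to discontinuation of blinded drug can stay.
- **SAP 7.1.5.2:** use the same bound in the partial-date rule. Because that rule compares months and years, the change matters only when the one-day shift crosses a month or year boundary.
- **SAP 7.1.6:** check the definition of treatment-emergent death, which uses the same bound.
- **SAP 3.8.2, 7.2.2.1 and 7.2.2.2:** leave the inclusive bound for laboratory and DXA assessments.
- **SAP 7.11:** add a sentence giving the reason for the AE bound.

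The cost is a wording change and one programming condition. The downside is that some switch-day AEs that began before the dose will leave the double-blind tables in both arms. An exception based on onset time may not be workable, since onset time is not among the AE data listed in Protocol 7.2. The listing flag keeps these events visible.
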